### Data source and cohort identification

The data source will be national (45-state) Medicaid Analytic Extracts data (2001-2010). The cohort will consist of adults who are 18 to 64 years old and diagnosed with schizophrenia who initiate a new psychotropic medication after a period of stable antipsychotic treatment. Individuals who are 65 or older because will be excluded because they also have Medicare and receive pharmacy benefits through Medicare Part D.

Schizophrenia will be defined as  $\geq 2$  outpatient claims or  $\geq 1$  inpatient claim for schizophrenia [ICD-9-CM: 295] during 365 days of consecutive Medicaid enrollment immediately prior to the index date. Stable antipsychotic monotherapy will be defined by filled prescriptions for only one second-generation antipsychotic (excluding clozapine), and no other psychotropics, for  $\geq 90$  days immediately preceding the start of the index medication (t0). After the  $\geq 90$  days of stable treatment with a single second-generation antipsychotic, study patients will have had a change in therapy defined as (1) addition of a second antipsychotic or (2) addition of a different psychotropic drug class (antidepressant, mood stabilizer, or benzodiazepine). To ensure the patients are in active treatment there must be an active supply of antipsychotic medication on t0.

The eligibility criteria select a cohort of individuals that are likely to have schizophrenia, have received antipsychotic monotherapy prior to the index date, and are still experiencing problems for which a new psychotropic medication strategy was initiated. A 1-year period of eligibility prior to follow-up initiation ensures sufficient time to collect service use related covariates to characterize cohort members.

Patients with stable clozapine monotherapy will be excluded because clozapine is largely reserved for the most severely ill patients. Patients who implement more than one change in therapy at the index date (e.g., addition of a mood stabilizer and an antidepressant) will also be excluded.

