### Comparators

Pharmacological treatment options for patients with schizophrenia who are nonresponsive to antipsychotic monotherapy will include (1) initiation of a second antipsychotic, (2) initiation of an antidepressant, (3) initiation of a mood stabilizer and (4) initiation of a benzodiazepine.

Within each clinical subgroup, treatment options may be refined by exclusions at the drug class or individual agent level. For example, antidepressants are generally not considered treatment alternatives in patients presenting with mania, but could reasonably be considered for patients in the remaining four schizophrenia subgroups: depression, anxiety, schizoaffective disorder, and uncomplicated schizophrenia. Unless it is not considered a reasonable treatment option for a specific subgroup, initiation of a new antipsychotic will serve as the reference category because it is a frequently recommended approach to improving treatment response and is a common treatment strategy across all of the clinical subgroups under study. A survey on the prescribing behaviors of clinicians who prescribe psychotropic medications for individuals with schizophrenia will inform these choices.

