## Follow-up and censoring

Follow-up will begin at the date of new treatment initiation (t0 or index date) and will end after 365 days regardless of changes in pharmacotherapy (intent-to-treat approach). We will also conduct secondary analyses using a 180-day follow-up period and an as-treated specification. In the as-treated approach, follow-up will end at discontinuation of the new treatment ( $>10$  days without drug) or addition of another psychotropic agent (antipsychotic, mood stabilizer, antidepressant, or benzodiazepine). All analyses will be censored at loss of Medicaid (because that is the data source) with one exception—in intent-to-treat mortality analyses, follow-up will not be censored at loss of Medicaid because date of death data comes from the Social Security Master File, not Medicaid.

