### Sample size

Table 5 presents sample size estimates for national 2001-2010 Medicaid data based on our preliminary analyses. For example, we expect that the following treatments with corresponding numbers will be options for the depression symptom subgroup: second antipsychotic (n = 2,192), mood stabilizer (n = 1,296), antidepressant (n = 4,646), and benzodiazepine (n = 1,199). We will then, for example, compare 2,192 patient episodes with a second antipsychotic to 2,192 propensity-score matched patient episodes that were treated with an antidepressant. The 1:1 matching method uses a nearest neighbor algorithm. As recommended for observational studies, we will use a caliper width of 0.2 of the standard deviation of the logit of the propensity score to ensure appropriate matching.

Our power analysis is based on two-sided ( $\alpha = .05$ ) tests for differences in proportions between treatment groups, which depend upon the sample size of each group and the probability of the outcome. To demonstrate power, we conservatively use the expected number of distinct patients rather than episodes (distinct patients equal approximately 70% of the episodes in Table 5). Final statistical analyses of individual episodes will have greater power (i.e., be able to detect even smaller percent differences) and will incorporate random effects to account for patients who contribute more than one episode.

Table 5: Estimated sample sizes of selected schizophrenia treatment episodes (2001-2010)

	Uncomplicated Schizophrenia	Schizoaffective Disorder	Depression	Mania	Anxiety
Second Antipsychotic	27,005	6,393	2,192	1,580	611
Mood Stabilizer	9,954	4,734	1,296	2,107	NA
Antidepressant	25,061	9,692	4,646	NA	1,110
Benzodiazepine	12,248	3,681	1,199	840	1,099

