#### AP treatment Initiation year

2002

2003

2004

2005

2006

2007

2008

2009

Diagnostic History, past year	ICD-9-CM Codes*
Depression	293.83, 296.2x, 296.3x, 296.9x, 298.0x, 300.4x, 311.xx
Anxiety	293.84, 300.0x, 300.2x, 300.3x, 308.3x, 309.21, 309.81, 313.0x, 313.2x, 313.89
Bipolar	296.xx (not 296.2x or 296.3x or 296.9x)
Substance use disorder	291.xx, 292.xx, 303.xx, 304.xx
Moderate/severe mental retardation	318.xx
HIV	042, 043, 044, 079.53, V08
Neoplasms	140.xx-239.xx (Exclude people with malignant neoplasms 140.xx-205.xx)
Diabetes	250.xx
Obesity	270.xx
Hyperlipidemia	272.0x-272.4x, 272.7x, 272.9x
White blood cell diseases	288.xx, 289.xx (exclude neutrophil d/o 288.00-288.04, 288.09, 288.1x)
Anemia	280.xx-285.xx
Drug-related dyskinesia	333.85
Hypertension	401.xx-405.xx
Ischemic heart disease	410.xx-414.xx
Pulmonary circulation diseases	415.xx-417.xx
Cardiac dysrhythmias	427.xx
Heart failure	428.xx
Cerebrovascular disease	430.xx-438.xx
Acute bronchitis and bronchiolitis	466.xx
Chronic bronchitis	491.xx
Pneumonia	480.xx-486.xx
Emphysema	492.xx
Asthma	493.xx
Appendicitis	540.xx-543.xx
Noninfectious enteritis and colitis	555.xx-558.xx
Diverticula of intestine	562.xx
Intestinal obstruction	560.xx
Chronic liver disease and cirrhosis	571.xx
Acute & chronic pancreatitis	577.0x, 577.1x
Cholelithiasis	574.xx
Acute kidney failure	584.xx
Chronic kidney failure	585.xx

Kidney infections	590.xx
Cellulitis and abscess	681.xx–682.xx
Osteoarthritis and allied disorders	715.xx
Intervertebral disc disorder	722.xx
Fractures, all sites	800.xx–829.xx
Fracture of neck of femur	820.xx
Poisoning by psychotropic medication	969.xx
Poisonings	960.xx–989.xx
Suicide and self-inflicted injury	E950-959
Intracranial injury	815.xx-854.xx
Severe cardiovascular diseases	401.0x-404.9x, 410.xx-416.xx, 425.xx-437.xx, 440.xx-447.xx
Schizophreniform	295.4x
Schizoaffective	295.7x

---

\* x indicates inclusion of any 5th digit if available for a diagnosis code.

xx indicates inclusion of any 4th and 5th digits if available for a diagnosis code.

Medication history, past year	Drug class
Psychotropic medication	
Antidepressants	SSRI/SNRI/mirtazapine, TCA and heterocyclic compounds, MAOI, trazodone-related antidepressants, bupropion
Mood Stabilizer	lithium, primary anticonvulsant, secondary anticonvulsant
ADHD medication	psychostimulants, alpha-agonists
Anxiolytic/hypnotics	benzodiazepines, GABA agonists, other newer or older anxiolytic/hypnotic

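### The propensity score has no measure of baseline antipsychotic supply during the 90-day run-in, and the run-in rule states no permitted gap

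*Combined protocol and SAP*

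**What the plan says.** The section on data source and cohort identification sets the entry rule: "Stable antipsychotic monotherapy will be defined by filled prescriptions for only one second-generation antipsychotic (excluding clozapine), and no other psychotropics". The period is at least 90 "days immediately preceding the start of the index medication (t0"). A further sentence adds a check on one day: "To ensure the patients are in active treatment there must be an active supply of antipsychotic medication on t0". For the 90 days themselves, the section gives no permitted gap, minimum number of fills or minimum share of days covered.

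From these criteria the same section concludes that cohort members "are still experiencing problems for which a new psychotropic medication strategy was initiated". The Comparators section introduces the four strategies as "Pharmacological treatment options for patients with schizophrenia who are nonresponsive to antipsychotic monotherapy".

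The only gap rule is in Follow-up and censoring. In the secondary as-treated analysis, "follow-up will end at discontinuation of the new treatment", meaning more than 10 days without drug, or at addition of another psychotropic.

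Appendix 2 lists past-year psychotropic history by class: antidepressants, mood stabilizers ("lithium, primary anticonvulsant, secondary anticonvulsant"), ADHD drugs, anxiolytics/hypnotics and other psychiatric drugs. For antipsychotic treatment it carries an initiation year. It lists no days covered and no supply gap for the baseline antipsychotic.

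**The concern.** The study asks what to add when symptoms persist despite antipsychotic treatment. A patient who had no supply for several weeks and then refilled has not clearly shown an incomplete response to the drug. If such patients can enter, the cohort is partly a different population from the one described, even if they are spread evenly over the four strategies.

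The comparison itself is affected only under a further condition. A recent lapse could plausibly influence which class the prescriber adds, and it could plausibly raise the risk of psychiatric admission, the primary outcome. It would then be a confounder that the score does not contain, although it can be computed from the fills that decide eligibility.

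**Working it through.** **1. Can a lapsed patient meet the entry wording?**

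Inputs: a 90-day run-in (days -90 to -1) and active supply on t0, both from the cohort section. The documents give no supply per fill, so 30 days is assumed. Coverage is the number of run-in days with supply divided by 90.

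| Fill days | Days covered | Longest gap (days) | Supply on t0 |
|---|---|---|---|
| -90, -10 | 30 + 10 = 40 (44%) | -60 to -11 = 50 | yes |
| -90, -1 | 30 + 1 = 31 (34%) | -60 to -2 = 59 | yes |
| -90, -29 | 30 + 29 = 59 (66%) | -60 to -30 = 31 | yes |
| -90, -45, -5 | 30 + 30 + 5 = 65 (72%) | -60 to -46 = 15 | yes |
| -90, -60, -30, 0 | 90 (100%) | 0 | yes |

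The first four rows show one antipsychotic and supply on t0. They qualify if fills during the period are enough. If the 90 days mean continuous supply, only the last row qualifies. A single 90-day fill on day -90 with a refill on t0 also gives 90 of 90 days and no gap, so the issue depends on fill length.

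**2. Would the score pick up a lapse?**

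Not directly. Appendix 2 does contain plausible correlates: substance use disorder, mental health emergency service, outpatient schizophrenia visits, psychiatric admissions and psychosocial contacts. Adjustment would therefore be partial. Run-in coverage needs days' supply on each fill. The active-supply check on t0 and the 10-day as-treated rule need the same field, so the plan already relies on it.

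**3. How large could the effect be?**

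The plan has no figure to reproduce. Assume lapse prevalence p1 in one arm and p0 in the other, a lapse that multiplies the admission hazard by k = 2, and a true hazard ratio of 1.0. At the start of follow-up the apparent ratio is

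(1 + p1(k - 1)) / (1 + p0(k - 1)).

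With p1 from 0.20 to 0.30 and p0 from 0.10 to 0.15:

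- 1.20/1.15 = 1.04 (smallest)
- 1.20/1.10 = 1.09
- 1.30/1.15 = 1.13
- 1.30/1.10 = 1.18 (largest)

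If the other arm had more lapses, the factor inverts, to 1.10/1.30 = 0.85 through 1.15/1.20 = 0.96. All of this is before any partial adjustment.

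**4. What would a restricted analysis cost in precision?**

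The Sample size section uses two-sided 0.05 "tests for differences in proportions between treatment groups" and distinct patients at 70% of episodes: 0.70 x 2,192 = 1,534; 0.70 x 1,199 = 839; 0.70 x 611 = 428. With equal groups and rates centred on 50% (assumed, since no base rate is given), the plan's differences of 5.0, 6.8 and 10.0 points have power 0.791, 0.796 and 0.834, close to its stated 80%. The difference detectable at 80% power is then about 1.98/√n. The share a gap restriction would remove is unknown; 10% and 40% are assumed.

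| Group (per arm) | Full cohort | 10% removed | 40% removed |
|---|---|---|---|
| Depression, 1,534 | 5.1 points | 5.3 | 6.5 |
| Depression, benzodiazepine, 839 | 6.8 | 7.2 | 8.8 |
| Anxiety, smallest group, 428 | 9.6 | 10.1 | 12.4 |

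Mania's smallest group is 840 episodes, about 588 patients (0.70 x 840), so it lies between the last two rows.

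**The case against.** The strongest reply is that treatment for at least 90 days naturally means continuous supply, in which case no lapsed patient enters. That reading is available, so the claim here is only that such patients could enter. The check on t0 does not settle it. The 90 days end before t0 and the change in therapy is an addition, so confirming that the first drug is still on hand has its own purpose.

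A reader might infer that the plan contradicts itself by calling one pattern stable before t0 and discontinued after it. The documents do not support that. The 10-day rule concerns the new treatment in a secondary as-treated analysis, and run-in and follow-up rules may differ.

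A reader might also infer that adding a second antipsychotic marks re-engagement with care. Every arm needs active supply of the original drug on t0, so a patient who lapsed and refilled has re-engaged in any arm. Nothing ties this to the reference category.

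The plan also has other defences: the correlates in Appendix 2, array analyses for unmeasured confounding, and an instrumental variable analysis if a suitable instrument is found. These stand as partial protection. The array approach addresses confounders that cannot be measured, however, and run-in coverage can be.

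Finally, a reader might ask for a dose-stability condition or a dose covariate. The plan uses stable to mean one drug and no other psychotropics and makes no claim about dose. Average dose is not comparable across agents without a conversion step. That is a debatable choice and is not pressed here.

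**Conclusion.** The point holds as an inexpensive improvement to confounding control, together with a request for clarification. The run-in rule does not say how gaps are handled, and the propensity score omits adherence to the baseline antipsychotic although the eligibility data can supply it. The label of non-response is weakened to whatever extent lapsed patients enter. Bias between arms additionally requires lapses to differ by chosen strategy and to affect admission. That is plausible, but the documents do not show it.

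The factor of 1.04 to 1.18 is illustrative. It rests entirely on the assumed prevalences and the doubled hazard, and takes no credit for the listed correlates. The documents do not support saying that such patients do enter in any given number, or that the primary cohort is wrongly defined.

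**What to change.** - In Appendix 2, add the proportion of the 90 run-in days covered by the baseline antipsychotic, the longest supply gap in that window, or both. The planned standardized differences will then show any imbalance between arms.
- Under Sensitivity Analyses, pre-specify an analysis of time to psychiatric hospitalization restricted to episodes with no run-in gap of more than 10 days, with the propensity score re-estimated in that set.
- In the cohort section, state how days' supply, overlapping fills and gaps are computed for the 90 days, and whether continuous supply is meant.

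Keep the primary cohort unchanged. A hard gap rule for eligibility would narrow a population meant to be generalizable and would reduce power in the main analysis.

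The cost is modest extra programming on pharmacy claims already used for eligibility. Precision is lost only in the restricted analysis, and matters most in the smaller subgroups (anxiety, mania, depression).

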### Secondary

We will also investigate time to index treatment discontinuation, time to introduction of another psychotropic medication, psychiatric emergency department visits, all-cause hospitalization, and death.

We will investigate adverse effects of medications including incidence of major cardiovascular events and diabetes mellitus.

Outcomes	
Death	Date of death will be defined by the Social Security Death Master File.
Psychiatric Hospitalization	Hospital claims will define inpatient admissions with a first listed mental disorder diagnosis (ICD-9:290-310). High levels of agreement between diagnoses in inpatient medical records and inpatient claims have been reported for several mental disorder groups, including schizophrenia (100.0%), major mood disorders (98.7%), alcohol dependence (97.8%), and drug dependence (96.4%). 
Psychiatric ED Visits	Emergency department claims are a reliable source of diagnostic information in relation to medical records and a valid source of illness severity information.  Emergency department visits in which the first listed diagnosis is a mental disorder (ICD-9-CM: 290-319) will be defined as emergency department mental health visits.
Self-Injurious Behavior	Deliberate self-harm will be defined by an E-code of E950-E958, excluding late effects of deliberate self-harm (E959), on any inpatient, emergency department, or outpatient claim. High positive predictive values have been reported. 
Diabetes Mellitus	One or more claims with a physician diagnosis of diabetes will define diabetes mellitus. Using self-reported diabetes status as the criterion standard, $\geq 1$ physician claim with any diagnosis of diabetes or a diabetes complication (ICD-9 codes: 295.00-2950.93, 357.2, 362.0-362.02, 366.41) has acceptable sensitivity (68.5%) and specificity (96.9%), and (kappa=0.76).  Sensitivity of 90% and specificity of 93% with self-reported diabetes. 
Cardiovascular Events:	Acute myocardial infarction (AMI) (ICD-9-CM: 410) or stroke (430-438, except 435) will be defined by diagnostic codes on inpatient claims of $\geq 3$ days in duration.  With this AMI definition 75% met criteria for definite or probable AMI on independent review of cardiac biomarkers, electrocardiograms, presenting symptoms, and medical history, and an additional 12% had a suspected AMI. 

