**CPT Codes for Psychotherapy or Psychosocial Service Contacts**

Services	CPT Codes
Psychotherapy	90804-90829, 90841-90847, 90849, 90853, 90855, 90857, 90875, 90876
Psychosocial Service Contacts	H0036, H2000, H2010, H2011, H2012, H2014, H2017

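### Baseline antipsychotic monotherapy is defined by filled prescriptions alone, so an antipsychotic injection billed as a procedure would be missed; the later exposure rules name no claim source

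*Combined protocol and SAP*

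**What the plan says.** - **Baseline** (Data source and cohort identification): "Stable antipsychotic monotherapy will be defined by filled prescriptions for only one second-generation antipsychotic (excluding clozapine), and no other psychotropics", for at least 90 days before the index drug. This is the only exposure rule that names its source.
- **Index date** (same section): the change in therapy is the addition of a second antipsychotic or of another psychotropic class, and "there must be an active supply of antipsychotic medication on t0". No claim type is given for either.
- **Reference arm** (Comparators): where it is a reasonable option for the subgroup, "initiation of a new antipsychotic will serve as the reference category".
- **Follow-up** (Follow-up and censoring): the primary analysis runs 365 days whatever happens to treatment. In the as-treated analysis "follow-up will end at discontinuation of the new treatment", meaning more than 10 days without drug, or when another psychotropic is added. No claim source or days-of-supply rule is given.
- **Secondary outcomes** (Secondary): these include "time to index treatment discontinuation, time to introduction of another psychotropic medication".
- **Procedure codes**: the only list, at the end of Appendix 2, is headed "CPT Codes for Psychotherapy or Psychosocial Service Contacts". It has no drug-administration codes.
- **Long-acting injections**: these appear only in a reference title, a trial of switching between injectable antipsychotics that the Goal section cites. No exposure rule mentions them.

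**The concern.** The study asks what to add once a single antipsychotic has proved insufficient. That question depends on each cohort member really taking one antipsychotic at t0. A rule that counts only filled prescriptions cannot register an antipsychotic that was never dispensed through a pharmacy claim. If clinics bill injected antipsychotics as administered-drug procedures, some patients already on two antipsychotics will meet the entry rule.

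If the later rules also use fills, the same gap affects follow-up. An injection added after t0 would not register as a new psychotropic in any arm. A patient whose index antipsychotic changes from tablets to an injection would appear to have stopped. That second error arises where the index drug is an antipsychotic, which is the reference arm for the comparisons.

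**Working it through.** **1. What follows from the text alone.** Take a patient who fills one oral second-generation antipsychotic for 90 days and receives a clinic injection of a different antipsychotic, billed as a procedure. Under the baseline rule as written, the fills show one antipsychotic and no other psychotropic, so the patient qualifies. The active-supply check at t0 is met by the oral drug. No other eligibility rule excludes the patient.

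**2. Whether adjustment could repair it.** The psychotropic history in Appendix 2 covers antidepressants, mood stabilizers, ADHD drugs, anxiolytics/hypnotics and a few other agents. It has no antipsychotic or injection variable; the antipsychotic initiation year is a calendar year only. Prior psychiatric admissions, mental health emergency services and schizophrenia visits are included. They adjust for some of the severity that may accompany injection use, but not for the second antipsychotic itself.

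**3. What follows only if fills also drive the later rules.**

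| Event | Recorded as | Analyses affected |
|---|---|---|
| Injection of a different antipsychotic added after t0, any arm | No added psychotropic | Time to another psychotropic; as-treated |
| Index antipsychotic moves from tablets to injection of the same drug | Discontinued after more than 10 days | Time to discontinuation; as-treated |
| Drug already injected before t0 is first filled as tablets | Second-antipsychotic start | Composition of the reference arm, all analyses |

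The discontinuation error does not touch the 365-day intent-to-treat analysis in Follow-up and censoring. It would reach the Aim 1 Cox models if the censoring sentence in the Analysis plan governs, because that sentence censors at discontinuation or change of drug. The two sections conflict and must be reconciled.

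**4. Size of the discontinuation error.** Let r be the share of second-antipsychotic starters who move to a procedure-billed injection of the same drug within the year, and s the share of those who would have stopped within the year anyway. The excess in recorded one-year discontinuation is r × (1 − s), so at most r. At an assumed r = 3% it is at most 3 percentage points in the reference arm. The documents give neither r nor s.

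**5. Illustration for the baseline error.** The plan's own figure comes first. In the depression subgroup, 70% of 2,192 episodes is 1,534 patients per group, with at least 80% power claimed for a 5.0-point difference. No base rate is given, so use 47.5% against 52.5% (the conservative case):

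power = Φ{[Δ√n − 1.96√(2·p̄(1−p̄))] / √[p₁(1−p₁) + p₂(1−p₂)]} = Φ{[0.05 × 39.17 − 1.386] / 0.706} = Φ(0.81) = 79.1%

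That reproduces the plan's figure to within a point. Now let an assumed share q of patients have a hidden injection of a different antipsychotic:

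| q (assumed) | Excluded from both arms: n per group | Power for 5.0 points | Left in: observed difference, 5.0 × (1 − q) | Power |
|---|---|---|---|---|
| 0% | 1,534 | 79.1% | 5.0 | 79.1% |
| 5% | 1,457 | 77.0% | 4.75 | 74.9% |
| 10% | 1,381 | 74.8% | 4.5 | 70.3% |
| 20% | 1,227 | 69.8% | 4.0 | 60.1% |

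The "left in" columns assume that a share q of the comparator arm carries the reference-arm risk. That is one scenario among several. Hidden patients could carry a different risk, or be spread unevenly over the arms, and the result would then differ.

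**The case against.** The strongest objection is that the billing premise is not in the documents. Nothing in them says that clinics bill injections as procedures, or how often. The Medicaid extract is not described as limited to pharmacy claims, so the programmers may already capture injections. This stands as a limit: the error is conditional and its size is unknown. It does not remove the point, because the baseline rule does name its source, and that source is fills.

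A reader might infer four stronger things that the documents do not support:

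- **That every exposure rule uses pharmacy claims only.** Filled prescriptions are named for the baseline rule. For the index drug, active supply, added psychotropic and discontinuation, the source is unstated.
- **That false discontinuations can occur only for antipsychotics.** The 10-day rule applies to every class, and late refills, leftover supply or inpatient stays can create false gaps in any arm. Only the tablet-to-injection mechanism is specific to antipsychotics.
- **That the as-treated results are biased in favour of the add-on arms.** More recorded stops in the reference arm is a clear direction for time to discontinuation. For hospitalization, a false stop is censoring. If patients who move to injections are at higher risk, censoring them would tend to favour the reference arm. The direction is uncertain.
- **That thousands of episodes are misclassified.** Multiplying the Table 5 total by an assumed injection rate would count same-drug injections as a second antipsychotic. It would also add subgroups that may overlap, since only the uncomplicated group is defined to exclude the others.

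**Conclusion.** The point holds as a weakness in the exposure definition. As written, the entry rule would admit a patient on two antipsychotics when one is injected and billed as a procedure. No other rule catches this and no covariate adjusts for it. This baseline error reaches the intent-to-treat primary analysis.

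The follow-up errors hold only if fills also drive the later rules. They then affect time to discontinuation, time to another psychotropic and the as-treated analyses, and the Aim 1 Cox models only if the Analysis plan's censoring sentence governs. Recorded discontinuation in the reference arm would be too high.

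Everything beyond the wording of the rule rests on the assumption that some clinic-given antipsychotics appear only as procedure claims. The table in the working illustrates a range and does not estimate the size.

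**What to change.** In Data source and cohort identification, the secondary outcomes and Follow-up and censoring:

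- Define antipsychotic exposure by pharmacy fills or drug-administration procedure claims for injectable antipsychotics, with a code list and a stated coverage period per claim. Apply it to baseline, index drug, active supply, added psychotropic and discontinuation.
- Exclude episodes with an injection claim for a different antipsychotic in the 90 days before t0.
- Count a first injection claim for a different antipsychotic as a second-antipsychotic start at t0, or as an added psychotropic during follow-up.
- Treat a change of formulation of the same drug as continuation.
- Report how many episodes each rule affects, by arm, and refresh Table 5.

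If the programming already does this, a short statement and the code list settle the matter. If the main definition cannot change, the minimum is a sensitivity analysis excluding patients with any such claim.

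The cost is a short code list and a re-run of the cohort programming; the extract is not restricted to pharmacy claims, so no new data source appears necessary. The exclusion makes the cohort smaller, slightly so if such claims are few. Counting injection starts, and patients treated by injection alone who now qualify, could add some episodes back, so the net change has to be counted.
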